### 3.0 STUDY DESIGN

#### 3.1 Study Phases

In this four-year study, we will enroll 480 self-reported HIV-negative or sero-status unaware, sexually active YMSM (ages 15-24) across three sites and randomize them into the GC intervention condition or to an attention-control condition. Primary outcomes will include (1) use of HIV prevention services (HIV testing, STI testing) and PrEP awareness and willingness. As secondary outcomes, we will assess PrEP use, sexual risk behaviors, and the linkage and retention in care among newly diagnosed HIV+ cases. We will also examine changes in GC's theorized mechanisms of change, including YMSM's attitudes, norms, self-efficacy, and behavioral intentions to adopt HIV prevention services.

Control condition: Participants randomized to the control condition will have access to the site locator portion of the Get Connected website, which includes information on HIV prevention services. While the provision of a test locator is a form (albeit weak) of an intervention, we felt that withholding referrals to testing and care services would be unethical given YMSM's vulnerability to HIV and STIs. Furthermore, given the availability of search engines to locate HIV/STI testing sites, the test locator condition may be considered usual care. Nevertheless, by providing the testing site locator only, we will be able to test the effect of the GC intervention condition (i.e., user-tailored content focused on HIV/STI testing and PrEP referral and the linkage to high-quality agencies) against the usual care control condition.

Intervention condition: Using a consensus approach to conceptualize health behavior change, the model guiding GC synthesizes The Integrated Behavioral Model and Self-Determination Theory as the theoretical underpinnings of our intervention. These theories emphasize social cognitive factors that impact behavior change and have informed HIV interventions. Consistent with these theories, GC content follows motivational interviewing (MI) principles by focusing on resolving ambivalence about HIV prevention behaviors, increasing self-efficacy for change, and enhancing motivation moving toward action. The intervention was developed by customizing content based on YMSM's psychosocial and sexual

profile (e.g., socio-demographics, HIV/STI testing history and testing motivations, recent sexual behavior, sources of support, self-reported values), as reported by participants' answers to their baseline assessment. At the individual-level, GC delivers tailored online content specific to each user's demographic characteristics (e.g., age, race/ethnicity, location, relationship status), HIV/STI risk behaviors (e.g., HIV/STI testing history; substance use; communication with partners regarding status) and sociocultural context (e.g., homelessness, incarceration). GC also employs tailoring at the systems-level. Participants across both conditions who report being tested since their last follow-up survey will be asked to complete a site assessment as part of their follow-up survey. Testing sites will receive biannual performance summaries that include aggregated participant scores from the site assessments, qualitative feedback participants provided, and their sites' scores in relation to other testing sites in their city. These summaries are provided in an effort to help sites understand their performance based on quality assurance evaluations from YMSM clients and to optimize service delivery if needed. The study team and Analytic Core will ensure that these summaries will not include any identifying information about participants.

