## 2.0 STUDY OBJECTIVES

As part of the U19 project, we propose to test the efficacy of Get Connected (GC) for increasing HIV-negative or sero-status unaware YMSM's successful uptake of HIV and STI testing willingness (HIV and STI testing). Given the overall low level of PrEP awareness and use among YMSM currently, we also include awareness of and willingness to use PrEP as a primary outcome (PrEP uptake during the trial will be measured as a secondary outcome). At the agency level, HIV/STI testing sites listed in GC will receive biannual performance assessments based on ratings that YMSM provide after visiting their locations. We will examine improvements in the quality of HIV test counseling and PrEP-related referrals to YMSM accessing local HIV/STI testing sites in the 3 cities selected to test GC.

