### 2.4 Study Hypotheses/Research Questions

- *Relative to the control condition, YMSM exposed to the GC intervention will report significantly greater increases in routine HIV/STI testing over a 12-month period. HIV testing will be the primary outcome for the trial.*
- *Relative to the control condition, YMSM exposed to the GC intervention will report increases in motivation around HIV testing (conceptualized as HIV/STI testing intentions, self-efficacy to engage in HIV/STI testing, and overcoming testing-related barriers).*
- *Relative to the control condition, YMSM exposed to the GC intervention will report significantly greater PrEP awareness and willingness to use PrEP).*

The primary analyses of the data from the Get Connected 2-parallel group randomized clinical trial will be performed according to the participants' original treatment assignment (i.e., intention-

to-treat analyses) and the inclusion of all data from all participants randomized in the final analysis.

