### **Binary outcomes such as HIV testing:**

The percentage of participants who report routine HIV testing over a 12-month period will be compared between the intervention arms (GC and the Control condition). Five assessments will occur at 1 month (visit window  $\pm$  1 month), 3 months ( $\pm$  1 month), 6 months ( $\pm$  1 month), 9 months ( $\pm$  1 month), and 12 months ( $\pm$  1 month). Repeated-measures analyses for HIV testing will be implemented by performing a generalized estimating equations (GEE) analysis via the SAS GENMOD Procedure (version 9.4; SAS Institute, Cary, NC) with an exchangeable correlation structure for the repeated measures within participant (binomial-logit model). The statistical model will include three predictors (intervention arm, time on study and the statistical interaction between intervention arm and time on study). The statistical model will provide estimates of the percentages of participants reporting HIV testing (plus 95% confidence intervals) by intervention arm and time on study. The model-based estimates are unbiased with unbalanced and missing data, so long as the missing data are non-informative (missing completely at random, MCAR). A P value  $\leq 0.05$  will be considered statistically significant for the main effects (intervention and time on study) and for the intervention by time on study interaction effect from the repeated measures analysis. **The statistical test for interaction between time on study and intervention arm will be the primary overall hypothesis test to determine whether HIV testing in the intervention groups changed in significantly different ways during follow-up (i.e., different temporal patterns over time).** If HIV testing rates in the two intervention groups are consistently different or similar (i.e., no statistical interaction) then the main effect test for intervention will be used as the primary test of intervention efficacy. If a significant interaction is detected, then Wald chi-square tests will be used to compare the differences between the model-based HIV testing estimates at each time interval and to compare differences over time within each intervention arm. Specific statistical tests will be done within the framework of the generalized linear model. All statistical tests will be 2-sided and unadjusted for multiple comparisons.

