The primary assessment for a difference between intervention arms for 'frequent tester' rates will be a two-sided Z-test for independent proportions with pooled variance. Confidence intervals (95%) will also be reported for the observed difference between the GC and control arms in 'frequent tester' rates. The same analysis plan described above will be used for the other primary outcomes that as binary (i.e., STI testing, PrEP awareness).

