### **Continuous outcomes such as Self-efficacy:**

Repeated-measures analyses for self-efficacy will be performed with a means model via the SAS MIXED Procedure (version 9.4; SAS Institute, Cary, NC), providing separate estimates of the means by time on study (at 5 scheduled assessments) and intervention group. The model will include three predictors (intervention arm, time on study and the statistical interaction between intervention arm and time on study). A compound-symmetric variance-covariance form in repeated measurements will be assumed for self-efficacy and robust estimates of the standard errors of parameters will be used to perform statistical tests and construct 95% confidence intervals. The model-based means are unbiased with unbalanced and missing

data, so long as the missing data are non-informative (missing at random, MAR). A P value  $\leq 0.05$  will be considered statistically significant for the main effects (intervention and time on study) and for the intervention by time on study interaction effect from the repeated measures analysis. **The statistical test for interaction between time on study and intervention will be the primary overall hypothesis test to determine whether self-efficacy in the two intervention groups changed in significantly different ways during follow-up (i.e., different temporal patterns over time).** If mean self-efficacy in the two intervention groups is consistently different or similar over time (i.e., no statistical interaction) then the main effect test for intervention will be used as the primary test of intervention efficacy. If a significant interaction is detected then t-tests will be used to compare the differences between the model-based intervention means at each time point and to compare differences over time within each intervention arm. Specific statistical tests will be done within the framework of the mixed effects linear model. All statistical tests will be 2-sided and unadjusted for multiple comparisons. The same analysis plan described above will be used for the other outcomes that are continuous (i.e., willingness to use PrEP).

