## 10.2 Power Estimates

10.2.1 The primary outcomes for the proposed trial are HIV-negative and HIV-unknown YMSM's successful uptake of HIV and STI testing willingness (e.g., HIV/STI testing), and PrEP awareness and willingness. For HIV testing, we define power as correctly identifying the difference in the proportion of YMSM who engage in HIV testing 2 or more times at least 3 months apart in the 12-month follow-up period ("frequent tester") in our treatment arm (GC) vs. our attention-control arm. For STI testing, we define it as receiving at least one STI test during the 12-month follow-up period. For proportions (e.g., HIV testing; PrEP awareness), our sample size calculations are based on a two-sample test of proportions using a two-sided significance level of 0.05. In order to have 80% power to compare GC to the attention-control group, we require at least 400 participants to find an absolute difference of 13% in cross-sectional analyses. Assuming within-person correlation of 0.25, we can detect an 8.8% difference. A less favorable within-person correlation of 0.75 allows us to detect an 11.3% difference.

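### Section 2.4 names HIV testing as the trial's primary outcome, sections 3.1 and 10.2 list four, all are tested unadjusted at 0.05, and no rule says which result makes the trial a success

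*Combined protocol and SAP*

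**What the plan says.** The combined protocol and SAP describes the primary outcome in several places, and they differ.

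- Section 2.4, opening hypotheses: "HIV testing will be the primary outcome for the trial". One outcome.
- Section 2.0: "we also include awareness of and willingness to use PrEP as a primary outcome". PrEP use is placed in the secondary tier in the same sentence.
- Section 2.4, binary outcomes: "The same analysis plan described above will be used for the other primary outcomes that as binary (i.e., STI testing, PrEP awareness". With HIV testing, that makes three.
- Section 2.4, continuous outcomes: "The same analysis plan described above will be used for the other outcomes that are continuous (i.e., willingness to use PrEP". PrEP willingness appears here without the label primary.
- Section 3.1: "Primary outcomes will include (1) use of HIV prevention services (HIV testing, STI testing) and PrEP awareness and willingness". Four outcomes, with PrEP use and sexual risk behaviour listed as secondary.
- Section 10.2: the primary outcomes are given as "successful uptake of HIV and STI testing willingness (e.g., HIV/STI testing), and PrEP awareness and willingness". The same four.

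The Study Abstract objectives, section 2.1 and section 10.1 also bundle HIV and STI testing with PrEP awareness and willingness, and section 10.1 speaks of primary outcomes in the plural.

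On error control, the binary and continuous parts of section 2.4 both set significance at P ≤ 0.05 and both state: "All statistical tests will be 2-sided and unadjusted for multiple comparisons". Section 10.2 adds that "our sample size calculations are based on a two-sample test of proportions using a two-sided significance level of 0.05". Sections 10.1 to 10.4 contain no hierarchy, split of alpha, gatekeeping order or definition of trial success.

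**The concern.** The question is what the trial's confirmatory claim is. The text supports at least three answers: HIV testing alone, the three outcomes that section 2.4 labels primary, or the four in sections 3.1 and 10.2. For the longer lists it does not say whether all must succeed or whether one is enough.

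Suppose HIV testing is null and PrEP awareness gives P = 0.03. Section 3.1 would support reporting success on a primary outcome. Section 2.4 would support reporting a trial that missed its primary outcome. Choosing between them once the data are known is not credible. If any one success is enough, the 0.05 in section 10.2 is no longer the error rate of the claim being made.

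The labels cannot be dismissed as loose wording about objectives. Sections 2.0 and 3.1 both separate a primary from a secondary tier and place PrEP awareness and willingness in the first.

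**Working it through.** **Inputs from the documents.** Two-sided alpha of 0.05 per outcome (sections 2.4 and 10.2); no adjustment (section 2.4, twice); four primary outcomes (sections 3.1 and 10.2) or three (section 2.4); 80% power, at least 400 participants and a 13-point absolute difference (section 10.2); 1:1 allocation (section 5.3).

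**Inputs assumed.** The control-arm rate and the correlation between outcomes. The documents give neither, so both are varied.

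**Step 1: the plan's own figure.** For two proportions with pooled variance, n per arm = [1.96·√(2·p̄·q̄) + 0.8416·√(p1·q1 + p2·q2)]² / d². With an assumed 25% against 38%, p̄ = 0.315 and d = 0.13:

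[1.96·√0.43155 + 0.8416·√0.4231]² / 0.0169 = (1.2876 + 0.5474)² / 0.0169 ≈ 199.3, so 200 per arm, 400 in total, with power 80.1%.

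Over control rates of 10% to 50% the total runs from 254 to 464. So 400 is attainable but cannot be confirmed without the control rate. What matters here is that it is a single comparison at 0.05, with no allowance for several primary outcomes.

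**Step 2: independent outcomes, one test each, no true effect on any.** P(at least one significant) = 1 − 0.95^k.

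- k = 4: 1 − 0.8145 = 18.5%
- k = 3: 1 − 0.8574 = 14.3%

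In the favourable direction only, k = 4 gives 1 − 0.975⁴ = 9.6%, against a nominal 2.5%.

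**Step 3: correlated outcomes.** For k test statistics with common correlation ρ and cut-off c = 1.96,

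P = 1 − ∫ φ(x)·[Φ((c − √ρ·x)/√(1−ρ)) − Φ((−c − √ρ·x)/√(1−ρ))]^k dx.

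| Assumed ρ | Four outcomes | Three outcomes |
|---|---|---|
| 0 | 18.5% | 14.3% |
| 0.3 | 17.4% | 13.6% |
| 0.5 | 15.6% | 12.5% |
| 0.7 | 13.0% | 10.9% |
| 0.8 | 11.4% | 9.8% |
| 0.9 | 9.4% | 8.4% |

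Unequal correlations (testing pair 0.5 to 0.8, PrEP pair 0.3 to 0.5, across pairs 0.1 to 0.5) give 14.7% to 17.6% for four outcomes.

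**Step 4: more than one test per outcome.** Section 2.4 tests the arm-by-time interaction first and, if there is none, the main effect of arm, each at 0.05. If the two tests are independent and either can yield a claim, one outcome carries 1 − 0.95² = 9.75%, and four independent outcomes carry 1 − 0.95⁸ = 33.7%. The further Z-test on frequent-tester rates is not counted. The table is therefore not an upper limit.

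**Step 5: the alternative of keeping four primary outcomes.** Bonferroni at 0.05/4 = 0.0125 gives 1 − 0.9875⁴ = 4.9%. Under the assumed 25% against 38%, power at 200 per arm falls from 80.1% to 61.9%, and 568 analysed participants would be needed in place of 400.

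**The case against.** The strongest reply is that section 2.4 has already settled the matter. It says in the singular which outcome is primary for the trial. On that reading there is no family of primary outcomes, and HIV testing is judged at its own level. This stands to the extent that the inflation is conditional. A reader might infer that the trial's false-positive rate simply is 13% to 19%. The documents do not support that: they never say that one success out of four is enough, the calculation also needs no true effect on any of the outcomes, and the 13% floor comes from stopping at an assumed correlation of 0.7.

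A reader might also infer that section 2.4 itself names four primary outcomes. It does not. It labels three and leaves PrEP willingness among other outcomes, which is a further inconsistency with sections 3.1 and 10.2.

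A second reply is that the PrEP outcomes were made primary on purpose, since section 2.0 justifies this by low PrEP awareness and use. That is fair. Demoting them is one remedy, and co-primary outcomes with Holm or a split of alpha would also resolve the conflict, at the cost shown in Step 5. What the documents require is a choice.

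Neither reply removes the contradiction. If the single-outcome sentence governs, sections 2.0, 3.1 and 10.2 and the binary part of section 2.4 are wrong as written.

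**Conclusion.** The contradiction stands in the current text, and nothing in the plan resolves it. Its numerical consequence depends on the reading. If any one primary outcome suffices and there is no true effect, the chance of a false positive lies between 18.5% (independent) and 9.4% (correlation 0.9) for four outcomes, and between 14.3% and 8.4% over the same range for the three labelled primary in section 2.4. These figures assume one test per outcome and equal correlations; the correlations are not from the documents, and the extra tests in section 2.4 could raise the figures. If HIV testing alone is primary, this inflation is absent and what remains is a labelling error in several sections. It should be corrected before results are seen, because it decides what may be claimed.

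**What to change.** Reconcile the sections before any results are seen. The cheapest route uses the sponsor's own sentence:

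1. Keep HIV testing as the sole primary outcome at two-sided 0.05, as the opening of section 2.4 states.
2. Relabel STI testing, PrEP awareness and PrEP willingness as key secondary outcomes in sections 2.0, 3.1 and 10.2 and in the binary part of section 2.4. Align the Study Abstract objectives, section 2.1, the continuous part of section 2.4 and section 10.1.
3. Test those three only after HIV testing succeeds, in a stated fixed order or with Holm.
4. Restrict the no-adjustment statement, in both parts of section 2.4, to exploratory outcomes.

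The gate needs one designated HIV-testing result. Which of the tests in section 2.4 supplies it is a separate matter that must also be settled.

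Cost: text changes only. HIV testing stays at 0.05, so the 400-participant calculation is unchanged. If HIV testing is not significant, none of the three can support a confirmatory claim. If it is significant, Holm requires the smallest of the three P values to be at or below 0.05/3 = 0.0167. A fixed order keeps 0.05 for each but makes each outcome depend on the one before it. If the sponsor prefers several primary outcomes, it should state the success rule and the alpha allocation, and revisit the sample size.

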### 6.1.2 On-study Evaluations/Measures

- *HIV Testing:* Follow-up surveys will repeat the HIV testing questions in each follow-up survey. The HIV testing outcome will be: the proportion of MSM tested for HIV two or more times at least 3 months apart in the 12-month follow-up period (“frequent tester”). As an additional analysis, we will also examine the proportions of participants who receive one HIV test.
  - Among self-reported newly diagnosed HIV+ cases, we will measure their linkage and engagement with appropriate medical care after initial diagnosis using criteria employed in prior ATN protocols with youth. We will define linkage as an HIV-related medical visit within 45 days of referral, and engagement as a second HIV-related medical visit within 16 weeks of initial visit. Onset of ART initiation, self-reported adherence to ART, and viral suppression are exploratory indicators, as we recognize that our follow-up period may not be a sufficient amount of time to see these changes.
- *STI Testing:* The STI testing outcome is defined as the proportion of YMSM tested for STIs at least once in the 12-month follow-up period. We will ask participants what STIs they have been tested for, the anatomic sites where they were tested, the date of their most recent STI test (if known), and whether a medical provider had diagnosed them with an STI. In the follow-up surveys, we will ask participants whether they had been tested for STIs in the past 3 months (for the 1-month follow-up survey, we ask about the past 30 days). If STI testing is reported, we will ask participants to indicate what tests they received, and whether they were diagnosed with an STI by a medical provider.
- *PrEP Use:* At each follow-up assessment, PrEP-eligible HIV-negative YMSM (per CDC guidelines) will be asked whether they have begun using PrEP. We will also ascertain if a provider recommended PrEP and/or were offered a prescription for PrEP.
 

*Site Evaluations:* Across both trial arms, YMSM who report testing in the prior 3 months will complete self-evaluation forms of their testing experiences to assess comfort, quality, and concerns after visiting a site for HIV/STI testing and PrEP prevention services. The assessment form is the same form used by the mystery shoppers. We will use these data to update the WebApp and to send aggregate data of YMSM's satisfaction with services to agencies biannually.

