## **10.0 STATISTICAL/ANALYTIC CONSIDERATIONS**

### **10.1 Introduction**

10.1.1 We will test the efficacy of GC in increasing HIV-negative or HIV-unknown YMSM's successful uptake of HIV and STI testing (e.g., routine HIV/STI testing) and increase in PrEP awareness and willingness, as compared to the attention-control condition over a 12-month period. Descriptive statistics of the psychosocial and demographic characteristics of the participants will be described for all and by intervention group. These will be compared between treatment groups using t-tests or Wilcoxon rank sum tests for continuous variables and chi-square tests for categorical variables. To test for intervention efficacy, we will conduct primary

analyses of our primary outcomes using regression analyses to compare our treatment group to the control using the appropriate link function (identity for continuous outcome, logit for binary outcome, and natural log for count outcomes). The regression will be run with group assignment only in the model, as well as, controlling for participants' socio-demographic characteristics, ATOD and psychological distress, and intervention-related process data (e.g., frequency of use, acceptability). Interactions between group assignment and these characteristics will be tested to explore potential moderators of treatment effect. We will repeat these analyses for the secondary outcomes (e.g., theoretical mediators)).

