## 11.3 Risks and Benefits

### 11.3.1 Risks

Some participants may be uncomfortable answering questions about their past sexual behavior and HIV-related behaviors. All information used in enrollment and recruitment describing the research activities will include a detailed description of the content and expected participation of the respondent, such that the respondent is aware of the nature of the questions and topics to be discussed. Respondents will complete their surveys online to maximize convenience and privacy. Informed consent documents will inform research participants of their rights as participants. During the consent process, participants will be reminded that they are free to refuse to participate in any study activities or choose to terminate their participation at any time. Our consent forms will also include information on limits of confidentiality (e.g., suicidal intent, homicidal intent, child abuse, etc.) and mandatory reporting requirements, which will be reviewed by all participants. While our surveys do not directly ask participants about child abuse or harm to others, it is possible that participants may volunteer this information. In such occurrences, we will follow established protocols used in our prior studies to assess risk level and follow-up appropriately.

Participants will provide their names and addresses or other personally identifying information as part of the study. There is a risk that these data could be unintentionally disclosed to someone not authorized to access the data, compromising the privacy of the participant. To reduce this risk, all contact information for the study participants will be kept in a password-protected location, with access restricted to the Study Coordinators and PIs.

Although we are not directly providing HIV testing, we are providing information on where participants can test for HIV in their locale. Participants who learn that they are HIV-positive or STI sero-positive may be distressed to learn of their health condition. This poses the greatest emotional and physical risk to participants in the research study. Given that our intervention seeks to link YMSM to HIV/STI testing locations, risks of distress are minimized by encouraging YMSM to receive their results at an agency that may offer counseling and referrals.

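### Linkage and retention in care are assessed only among newly diagnosed men, a group whose make-up depends on arm, so an arm comparison within it is not protected by randomisation

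*Combined protocol and SAP*

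**What the plan says.** Section 3.1 names as a secondary outcome "the linkage and retention in care among newly diagnosed HIV+ cases". Section 6.1.2 keeps the same denominator: "Among self-reported newly diagnosed HIV+ cases, we will measure their linkage and engagement with appropriate medical care after initial diagnosis". It then defines the first of the two steps: "We will define linkage as an HIV-related medical visit within 45 days of referral". The later step has its own time limit, counted from the first visit: "engagement as a second HIV-related medical visit within 16 weeks of initial visit". What 3.1 calls retention appears in 6.1.2 as engagement. Neither section gives a version with all randomised men as the denominator.

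Section 10.1 describes the efficacy analysis of the primary outcomes as "using regression analyses to compare our treatment group to the control", run unadjusted, adjusted and with moderator interactions. It then adds: "We will repeat these analyses for the secondary outcomes". The only example in that sentence is theoretical mediators, but nothing exempts linkage.

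Two further statements decide who can be diagnosed. Section 2.4 hypothesises that "YMSM exposed to the GC intervention will report significantly greater increases in routine HIV/STI testing over a 12-month period". Section 11.3.1 begins a sentence on risk with "Although we are not directly providing HIV testing". The intention-to-treat statement in 2.4 is made for the primary analyses.

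Section 8.4 (item 8.4.5) discontinues an RCT participant who reports an HIV-positive diagnosis, and the text that follows the list stops data collection from the date of discontinuation.

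**The concern.** Entry HIV status is self-reported (section 4.1) and the study tests nobody, so a man is newly diagnosed only if he chooses to test during follow-up. Testing is the behaviour GC is designed to change. If GC works, its diagnosed group contains men who would have stayed undiagnosed under control. The two diagnosed groups then differ in composition for a reason other than chance, and covariate adjustment cannot be relied on to restore comparability.

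A regression of linkage on arm within this group mixes any real effect of GC on linkage with a change in who is being counted. The problem grows with the success of the intervention on its primary outcome. At stake is a secondary result that could be read as GC harming, or helping, linkage when it shows neither.

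**Working it through.** **1. The plan's own figures.** The documents give no expected number of diagnoses, sample size or power for linkage. The only sizing figure is in section 10.2: 400 participants for a 13-point difference, 80% power, two-sided 0.05, control rate not stated. With

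n per arm = [1.96√(2p̄(1−p̄)) + 0.842√(p₁(1−p₁)+p₂(1−p₂))]² / (p₁−p₂)²

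and assumed rates of 25% and 38%, n = (1.288 + 0.547)² / 0.13² = 199.2, so 200 per arm and 400 in total. This pair is consistent with the plan, but the base rate is an assumption. It is borrowed below as the testing rate, although the plan's figure concerns frequent testing, a stricter measure than the single test that a diagnosis needs.

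**2. Inputs.** From the documents: 240 per arm (sections 3.4 and 5.3) and the 13-point difference (10.2). Assumed: 5% undiagnosed infection (12 men per arm); testing 25% control and 38% GC; linkage 80% in men who would test anyway; a rate r in men who test only because of GC; no direct effect of GC on linkage.

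**3. Formulas.**
- Control: diagnosed = 12 × 0.25 = 3.0; linked = 3.0 × 0.80 = 2.4, which is 80% of the diagnosed and 2.4/240 = 1.00% of those randomised.
- GC: diagnosed = 12 × 0.38 = 4.56; linked = 2.4 + 12 × 0.13 × r = 2.4 + 1.56r.

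**4. Results for GC.**

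| r | Linked (n) | Linked among diagnosed (control 80%) | Linked among randomised (control 1.00%) |
|---|---|---|---|
| 80% | 3.65 | 80% | 1.52% |
| 60% | 3.34 | 73% | 1.39% |
| 40% | 3.02 | 66% | 1.26% |
| 20% | 2.71 | 60% | 1.13% |

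The shift in the among-diagnosed percentage is (0.13/0.38) × (r − 80%) = 0.342 × (r − 80%). At r = 40% it is −14 points. At the ceiling of r = 100% it is 0.342 × 20 = +7 points. GC looks worse while linking more men whenever r lies above zero and below the rate in men who would test anyway. Changing the undiagnosed prevalence from 2% to 10% leaves these percentages alone and moves the expected diagnoses to 1.2–6.0 (control) and 1.8–9.1 (GC).

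**5. A second set of assumptions.** Take 12 undiagnosed men per arm, 40% v 60% diagnosed, linkage 85% in men diagnosed anyway and 50% in the extra men. Control: 4.8 diagnosed, 4.1 linked (85%). GC: 7.2 diagnosed, 4.08 + 12 × 0.20 × 0.50 = 5.3 linked (73%). If the increase in diagnosis is 13 points instead of 20, GC is (4.08 + 0.78)/6.36 = 76%.

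**6. Precision among the diagnosed.** The 95% half-width is 1.96√(2 × 0.75 × 0.25/n): 54, 45 and 38 points for n = 5, 7 and 10 per arm. This large-sample formula is crude at such counts. Power for 80% v 66% is about 7% at 5 per arm and 10% at 10 per arm; 80% power needs about 164 diagnosed men per arm.

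**7. All-randomised version.** On the step 5 figures, 4.1/240 v 5.3/240 is 1.7% v 2.2%, a difference of 0.5 points with half-width 1.96√(0.017 × 0.983/240 + 0.022 × 0.978/240) = 2.5 points. At 200 per arm with 1% in control, the detectable difference is about 5 points.

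**8. Whether the outcome can be observed.** Engagement can take 45 + 112 = 157 days from referral. Surveys after month 3 are three months apart (section 8.1). Under 8.4 the report of the diagnosis itself triggers discontinuation and the end of data collection. Sections 3.1 and 6.1.2 require data from after that point.

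**The case against.** The strongest reply is that no sentence says linkage will be compared between arms. Sections 3.1 and 6.1.2 speak of assessing and measuring it, the hypotheses in 2.4 omit it, and the sentence in 10.1 gives only mediators as its example. This stands in part: the comparison is implied. But 3.1 lists linkage as a secondary outcome, and 10.1 repeats the arm regressions for secondary outcomes without exception, so an analyst following the text would run it.

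A reader might infer that GC creates the diagnosed group. The documents do not support that: control men also have the site locator, also test and are also diagnosed. GC would enlarge the group and change its mix.

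A reader might also infer that GC will look worse. Nothing in the documents says that men drawn into testing by GC link less often, and section 3.1 describes GC as linking men to high-quality agencies through ranked sites, which could raise linkage. The sign of the distortion comes wholly from the assumed rates.

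A misleading significant result is also unlikely: a 12- to 14-point distortion sits well inside the intervals in step 6.

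Finally, the all-randomised outcome is no clean substitute. It restores the randomised comparison, but it combines infection, testing and linkage. GC also promotes PrEP, and fewer infections in GC would lower the outcome and make prevention look like failure. This objection stands and shapes the fix.

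**Conclusion.** The point holds in a limited form. As written, the plan leads to an arm comparison within a group formed after randomisation, and the intervention is intended to change who belongs to it. That comparison is not protected by randomisation and could err in either direction. The illustrations give 80% v 66% or 85% v 73% among the diagnosed while GC links more men. Every rate in them is an assumption, and the distortion vanishes if the extra testers link as often as the others.

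With probably a handful of cases per arm, the realistic consequence is a secondary estimate that cannot be interpreted. The primary HIV testing result is unaffected. The conflict between section 8.4 and sections 3.1 and 6.1.2 is more immediate: until it is resolved, linkage and engagement may not be observed in either arm, whichever denominator is used.

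**What to change.** 1. In section 10.1, exclude linkage and retention among the diagnosed from the regressions repeated for secondary outcomes. State in 3.1 and 6.1.2 that they will be reported as counts by arm (diagnosed, linked, engaged) without an efficacy test.
2. If an arm comparison is wanted, define it as 'newly diagnosed and linked within 45 days' (and likewise 'and engaged within 16 weeks of the first visit') out of all randomised men, and label it descriptive. State that it combines infection, testing and linkage, so that fewer infections in GC would lower it.
3. For that outcome, give a rule for diagnosed men whose linkage or engagement is not observed, including those diagnosed too late for the window to close. Section 10.4 offers only general imputation options, and coding such men as not linked would count discontinuation or late diagnosis as failure.
4. Reconcile section 8.4 with sections 3.1 and 6.1.2 on what is collected after a reported positive diagnosis.

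Item 1 costs only wording. Items 2 and 3 also need only wording, but they are useful only if the data exist. The cost of item 4 depends on how the sponsor resolves the conflict, so it cannot be assumed that no change to data collection is needed.
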